### **Purpose and background**

[figure not shown]
#### **Scientific objectives**

The objective of this study is to evaluate the performance of a miniaturized sleep apnea test, called NightOwl. The system consists of a sensor placed on the fingertip and a cloud-based analytics software. The sensor acquires accelerometer and photoplethysmographic data. The software derives actigraphy from the former, and blood oxygen saturation and peripheral arterial tone (PAT), among other features, from the latter. In order to assess NightOwl's performance, we will compare the respiratory event index (REI), defined as the number of respiratory events per hour of sleep, derived by the NightOwl system, to the AHI obtained from manual analysis of the polysomnography (PSG), which is the gold standard for sleep apnea diagnosis. We will also compare the total sleep time (TST) derived by both systems. This study will be performed in a sleep lab environment.

As of March 2017, the new clinical practice guideline for diagnostic testing for adult sleep apnea of the American Academy of Sleep Medicine (AASM) for the first time formulates a strong recommendation that both polysomnography (PSG) and home sleep apnea testing (HSAT) are appropriate diagnostic testing options for uncomplicated adult patients who are at increased risk of moderate to severe sleep apnea.

Collop et al. performed a comprehensive analysis of the evidence for HSAT devices to diagnose obstructive sleep apnea (OSA) in out-of-center settings. The authors concluded that testing devices that analyze changes in peripheral arterial tone (PAT) in combination with actigraphy and blood oxygen saturation (SpO2) are adequate to diagnose OSA in patient populations with a high pre-test probability.

In this study, we wish to assess the performance of a system for the diagnosis of OSA that measures and analyzes the abovementioned parameters, called NightOwl. The system consists of a small sensor device which is placed on the fingertip and a cloud-based analytics platform. An illustration of the NightOwl sensor can be found in Figure 1.

**Figure 1: A photograph of the NightOwl sensor positioned on the index finger (source: <https://www.resmed.com.au/sleep-apnea/sleep-study>)**

It is designed to be self-applied and initiated by the patient by attaching the sensor to the fingertip by means of an adhesive patch.

#### Justification for involving humans

In order to investigate whether the NightOwl achieves adequate performance in deriving the REI, we need to apply it to subjects that are undergoing a simultaneous polysomnography study, which is the gold standard for sleep apnea diagnosis.

#### Subjects

##### Number of subjects

100

##### Gender of subjects

No gender specific bias will be introduced in recruitment, such that the subject sample will approximate the gender distribution of subjects admitted to a sleep clinic for an overnight PSG. From previous clinical trials, we expect the gender distribution to be approximately 60% male and 40% female. We do not exclude pregnant women from participating in the study since we

want to represent this population in our subject pool. As justified below, the NightOwl sensor poses negligible risk for the subject, pregnant or otherwise.

#### Subjects age

We aim to include subjects from the age of 13 and older. The American Academy of Sleep Medicine (AASM), which is the leading guideline body in sleep medicine, recommends using the adult criteria for the scoring of respiratory events for young adolescents of at least 13 years of age. The AASM recognized that this recommendation would provide the underserved adolescent population greater access to sleep studies. Hence in order to represent the full age range of subjects for which the adult scoring rules apply, and for which we want to validate our device, we aim to include subjects of 13 years of age and older.

#### Racial and Ethnic Origin

We aim to include sufficient enrollment of persons of diverse racial and ethnic backgrounds. We will not stratify the subject population on a racial or ethничal basis but will assume that the subjects population without stratification will represent subjects of a diverse racial/ethnic background because of the significant subject pool size.

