**Figure 2 - Flowchart of study. Experimental signifies procedures that are performed exclusively for research purposes.**

#### Frequency and duration

We aim to include between 10 and 19 subjects every study night. Each patient has one night of recording.

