#### Detailed procedure for each study night

For every patient scheduled for an overnight in-lab PSG, the clinical personnel in charge of administering the PSG will assess whether the patient is eligible for inclusion (does not violate the exclusion criteria) to the study (the patient passes the inclusion criteria since he/she has been scheduled for a PSG). Every eligible patient will be presented with the ICF. The patient can at all time ask for clarifications on the content of the ICF and will be provided with sufficient time to read the entire form. Upon signing of the ICF, the patient will be included in the study. For subjects aged under 22, parental consent is required.

For each subject included during a particular night, the age, gender, height, and weight will be collected. Additionally, we will ask the subject for a self-report of his/her race and ethnicity. The following options will be provided:

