### **Ethnicity Data Standard**

Are you Hispanic, Latino/a, or of Spanish origin? (One or more categories may be selected)

- a.  No, not of Hispanic, Latino/a, or Spanish origin
- b.  Yes, Mexican, Mexican American, Chicano/a
- c.  Yes, Puerto Rican
- d.  Yes, Cuban
- e.  Yes, Another Hispanic, Latino/a or Spanish origin

These categories roll up to the Hispanic or Latino category of the OMB standard

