### **Race Data Standard**

What is your race? (One or more categories may be selected)

- a.  White
- b.  Black or African American
- c.  American Indian or Alaska Native
- d.  Asian Indian
- e.  Chinese
- f.  Filipino
- g.  Japanese
- h.  Korean
- i.  Vietnamese
- j.  Other Asian
- k.  Native Hawaiian
- l.  Guamanian or Chamorro
- m.  Samoan
- n.  Other Pacific Islander

These categories are part of the current OMB standard

These categories roll up to the Asian category of the OMB standard

These categories roll-up to the Native Hawaiian or Other Pacific Islander category of the OMB standard

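### Does expecting racial and ethnic diversity from a pool of 100, with no planned table of who was enrolled, call for a change to the plan?

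*Combined protocol and SAP*

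**What the plan says.** Number of subjects gives 100, without a derivation. Racial and Ethnic Origin states an aim, "We aim to include sufficient enrollment of persons of diverse racial and ethnic backgrounds", puts no figure on what is sufficient, and says the sponsor "will assume that the subjects population without stratification will represent subjects of a diverse racial/ethnic background because of the significant subject pool size".

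For gender the plan argues differently. Recruitment without selection means that "the subject sample will approximate the gender distribution of subjects admitted to a sleep clinic for an overnight PSG", and an expected split of about 60% male and 40% female is given. For age, the plan notes that adult scoring rules apply from 13 and describes the range as one "for which we want to validate our device, we aim to include subjects of 13 years of age and older".

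The sections on the nightly procedure and the acquired dataset have age, race and ethnicity recorded for each subject. The race and ethnicity form follows an FDA guidance, and its detailed options map to standard groups, for example "These categories roll up to the Hispanic or Latino category of the OMB standard" and "These categories roll up to the Asian category of the OMB standard". Study analysis lists two main performance analyses: Pearson correlation for the respiratory event index and total sleep time, and agreement on severity category. Neither is broken down by age, race or ethnicity, and no demographic table is mentioned.

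**The concern.** Three things look wrong together.

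- Pool size is offered as the reason for diversity, but size does not set the mix. If a centre books few patients from a group, its expected share stays small at any sample size.
- An aim of sufficient enrolment without a number cannot be checked.
- Admitting patients from 13 upwards permits adolescents but does not ensure that any take part.

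With no planned table by age, race or ethnicity, a report could describe the device as validated from 13, or the sample as diverse, with few or no such subjects behind the statement. What is at stake is the scope of the conclusions. The estimates of correlation and agreement are not affected.

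**Working it through.** **Inputs.** The sample size of 100 is from Number of subjects. The documents give no share for any racial, ethnic or age group among booked patients, so shares *p* from 1% to 20% are assumed. The plan has no figure of its own on this point to reproduce.

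**1. Does size help presence?** The chance that a group with share *p* is absent from *n* subjects is (1 − *p*)^*n*. With *n* = 100:

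| Assumed share | Calculation | Chance of none |
|---|---|---|
| 1% | 0.99^100 | 37% |
| 2% | 0.98^100 | 13% |
| 3% | 0.97^100 | 4.8% |
| 5% | 0.95^100 | 0.6% |

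The share at which presence has a 95% chance is 1 − 0.05^(1/100) = 0.0295, or about 3%. At a 5% share the chance of at least one subject rises from 92.3% with 50 subjects to 99.4% with 100. Size does what the plan says, as far as presence goes.

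**2. Does size set the mix?** No. The expected count is *np*, so the expected share is *np*/*n* = *p* at every *n*. A 5% group is expected to supply 2.5 of 50, 5 of 100 or 20 of 400.

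**3. Does presence mean useful numbers?** Binomial upper tails with *n* = 100:

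| Assumed share | Expected count | 5 or more | 10 or more |
|---|---|---|---|
| 2% | 2 | 5.1% | under 0.1% |
| 5% | 5 | 56% | 2.8% |
| 10% | 10 | 98% | 55% |
| 20% | 20 | over 99.9% | 99.8% |

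**4. What could a small group show?** Assume 80% agreement on severity category. The exact 95% interval is 44% to 97% for 8 of 10, against 71% to 87% for 80 of 100. Breaking results down would add rows that say little.

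**5. What does the text commit to?** The sections on age and on racial and ethnic origin speak of what the sponsor aims for and assumes. Neither fixes what the report will conclude. Study analysis calls its two items the main ones, which leaves room for an ordinary description of the sample. Age, race and ethnicity are collected for every subject, on a form whose roll-up to standard categories is already printed. An analyst can produce the counts without new data or a new rule. The gender paragraph and the race paragraph also rest on the same recruitment: every eligible booked patient is offered consent, with no stratification. Only the reason given differs.

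**The case for a change.** The strongest case for a change is that it would cost little and that timing matters. The diversity paragraph could say, as the gender paragraph does, that the sample will reflect the patients booked. One table of counts by age group, race and ethnicity could be promised, with the number of adolescents stated beside any conclusion for 13 and older. A routine table prepared later carries no rule, fixed in advance, on how many subjects a group needs before a conclusion covers it.

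The criticism of the wording stands: bookings, and not size, set the mix. It also stands that the plan writes down no such table and that scoring rules valid from 13 do not show that adolescents were enrolled.

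The rest does not carry a change. The table is what any competent report of this study would contain. A rule on minimum numbers needs choices on which the documents offer no guidance: a minimum count, and an upper age for adolescents. The only other age line in the plan, "For subjects aged under 22, parental consent is required", serves consent and not analysis. Such a rule could also work against its purpose. With a minimum of 10, a group at a 5% share would qualify only 2.8% of the time, so small groups would nearly always be left out of the conclusions. Hiding small cells would make zero look the same as nine, which is the very information wanted.

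**Conclusion.** No change is called for. The paragraph on racial and ethnic origin gives a poor reason for a reasonable expectation, and the missing table is a gap that analysts fill as a matter of course from data the plan already collects.

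Presence of groups with a share of about 3% or more is likely with 100 subjects. Rarer groups may be missed, and a group at 5% will seldom reach 10. These figures rest on assumed shares and on treating subjects as independent draws from one pool of bookings; the documents give neither the shares nor the split among centres.

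The two main analyses are valid for whatever mix is enrolled. The remaining risk is a report that claims more about adolescents or minority groups than its numbers support. The plan does not commit to such a claim, and the ordinary table of subject characteristics would let a reader see it. The conclusion applies to the public text, in which no demographic table was found.

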#### Inclusion criteria

Subjects with an indication for an in-lab polysomnography

#### Exclusion criteria

Intellectually disabled people

People younger than 13 years of age.

#### Vulnerable Subjects:

Children aged 13 or older will not be excluded (rationale provided in the *Subjects age* paragraph). Explicit consent of the parents will be required before inclusion.

Pregnant women will not be excluded (rationale in the *Gender of subjects* paragraph).

### **Methods and procedures**

[figure not shown]
#### Overview of study design and procedures

The study is open-blind and non-randomized.

During the PSG night:

- Eligible patients will be invited to participate in the study and will be presented with the ICF.
- If the ICF is accepted, the patient will undergo the scheduled in-lab PSG, in which the NightOwl sensor will be included.

During each study night, the following flowchart will be followed:

**Figure 2 - Flowchart of study. Experimental signifies procedures that are performed exclusively for research purposes.**

#### Frequency and duration

We aim to include between 10 and 19 subjects every study night. Each patient has one night of recording.

#### Precautions

No procedures, situations, or materials are deemed hazardous; hence no specific precautions are to be exercised. See NightOwl Product Risk Analysis (attached)

#### Sample collection

Data of the PSG and NightOwl will be collected throughout the entire duration of the overnight PSG study.

#### Detailed procedure for each study night

For every patient scheduled for an overnight in-lab PSG, the clinical personnel in charge of administering the PSG will assess whether the patient is eligible for inclusion (does not violate the exclusion criteria) to the study (the patient passes the inclusion criteria since he/she has been scheduled for a PSG). Every eligible patient will be presented with the ICF. The patient can at all time ask for clarifications on the content of the ICF and will be provided with sufficient time to read the entire form. Upon signing of the ICF, the patient will be included in the study. For subjects aged under 22, parental consent is required.

For each subject included during a particular night, the age, gender, height, and weight will be collected. Additionally, we will ask the subject for a self-report of his/her race and ethnicity. The following options will be provided:

### **Ethnicity Data Standard**

Are you Hispanic, Latino/a, or of Spanish origin? (One or more categories may be selected)

- a.  No, not of Hispanic, Latino/a, or Spanish origin
- b.  Yes, Mexican, Mexican American, Chicano/a
- c.  Yes, Puerto Rican
- d.  Yes, Cuban
- e.  Yes, Another Hispanic, Latino/a or Spanish origin

These categories roll up to the Hispanic or Latino category of the OMB standard

### **Race Data Standard**

What is your race? (One or more categories may be selected)

- a.  White
- b.  Black or African American
- c.  American Indian or Alaska Native
- d.  Asian Indian
- e.  Chinese
- f.  Filipino
- g.  Japanese
- h.  Korean
- i.  Vietnamese
- j.  Other Asian
- k.  Native Hawaiian
- l.  Guamanian or Chamorro
- m.  Samoan
- n.  Other Pacific Islander

These categories are part of the current OMB standard

These categories roll up to the Asian category of the OMB standard

These categories roll-up to the Native Hawaiian or Other Pacific Islander category of the OMB standard

**Table 1: Self-reported options for Ethnicity and Race**

The NightOwl sensor will be attached to the middle finger of the hand on which the pulse oximeter of the PSG is applied by means of a disposable adhesive fingerwrap. The NightOwl sensor will be switched on and connected to a smartphone on which the NightOwl Companion App is installed. The NightOwl Companion App continuously acquires the raw sensor data from the NightOwl Sensor and stores this data on its internal memory. After starting the acquisition of the NightOwl sensor data via the NightOwl Companion App, the PSG recording can be started.

When the personnel press the ‘Wake up’ button in the NightOwl Companion App at the end of the PSG study, the data will be uploaded to a secure cloud server in which the raw NightOwl Sensor data is stored and on which the NightOwl Software, which analyses the data, is deployed.

After pressing the ‘Wake up’ button in the NightOwl Companion App, the PSG equipment and NightOwl sensor will be detached from the subject. The NightOwl Sensor will be disinfected and cleaned. The following disinfectants can be used on the sensor:

- Mikrozid
- Clorox
- Lysol
- Cavicide
- 70% Ethyl alcohol or isopropyl alcohol (IPA)

### Details of acquired dataset for each subject

Throughout the study, the following data will be collected for each included subject:

- Polysomnographic data (EDF format), by means of export from the sleep clinics' PSG software
- Respiratory events and sleep stages annotated by the sleep technician (EDF, TXT, or CSV format), by means of export from the sleep clinics' PSG software
- NightOwl sensor data, by means of export from the NightOwl database:
  - red and infrared PPG from finger (CSV)
  - accelerometry from finger (CSV)
- Subject's age, gender, weight, height, self-reported ethnicity, and self-reported race will be collected right before administering the PSG.

### Potential risks

#### Risk Category

The NightOwl sensor has been tested against IEC 60601-1 (Medical Device Electrical Safety) and IEC 60601-1-2 (Medical Device Electromagnetic Compatibility) standards. It is a low voltage device that contains an accelerometer and an optical sensor such as would be found in a traditional pulse oximeter. In the FDA guidance document “Pulse Oximeters - Premarket Notification Submissions [510(k)s]” it is stated that generally, FDA believes pulse oximeters addressed by this guidance document are non-significant risk devices.

The Product Risk Analysis, conducted in accordance with ISO14971:2012; Application of Risk Management to Medical Devices, is attached. There are no residual risks that considered to be unacceptable.

Hence, risk of the research is considered **minimal**. the probability and magnitude of harm or discomfort anticipated in the research are not greater than those ordinarily encountered in daily life or during the performance of routine physical or psychological examinations or tests.

#### Potential Risk and protection against such risk

A non-serious risk for cytotoxicity or skin irritation caused by the sensor material being in continuous contact with the fingertip for the overnight recording could be identified. However, this risk is deemed negligible since the sensor enclosure material passed ISO10993-1 compliant tests for cytotoxicity and Direct Primary Skin Irritation.

A risk for discomfort of the subject caused by the tight application of the NightOwl sensor to the finger exists. In order to mitigate this risk, the subject will be explicitly encouraged to either contact the clinical personnel to reapply the sensor more loosely or to detach the sensor from the finger.

#### Potential Benefit

There is no potential benefit for individual subjects

#### Subject identification, recruitment, and consent/assent

For every patient scheduled for an overnight in-lab PSG, the clinical personnel in charge of administering the PSG will assess whether the patient is eligible for inclusion (does not violate the exclusion criteria) to the study (the patient passes the inclusion criteria since he/she has been scheduled for a PSG). Every eligible patient will be presented with the ICF. The patient can at

all time ask for clarifications on the content of the ICF and will be provided with sufficient time to read the entire form. The protocol will be discussed with the subject, all questions will be answered. The subject will explicitly be asked if all content was clear.

Upon signing of the ICF, the patient will be included in the study. For patients aged under 22, parental consent is required and both parent and child will be asked if all content was clear. The consent forms will be stored. All ICFs will be entered into the IRB's storage system in unlocked word form.

The subject will incur no extra cost as a result of participating in the study.

#### Compensation of subjects

The subjects will receive no payment for participating in the study

### **DATA AND CONFIDENTIALITY**

#### HIPAA Compliance

This study will be conducted in full accordance the HIPAA privacy rule. Any episodes of non-compliance will be documented. The investigators will perform the study in accordance with this protocol and will obtain consent (unless a HIPAA waiver of Consent is granted) and will report unexpected problems in accordance with institutional regulatory committee. Collection of data will be accurate and will ensure the privacy, health, and welfare of research subjects during and after the study. The principal investigator overseeing the conduct of this study and the research personnel will comply with the applicable federal, state, and local regulations governing clinical research and the protection of human research subjects.

#### Study analysis

Two main performance analyses will be performed:

- The evaluation of the Pearson correlation between the REI and TST estimate obtained from the NightOwl and the AHI and TST determined from the PSG;
- The evaluation of the agreement between patient categorization (into sleep apnea severity categories) obtained by the NightOwl and those obtained by the manual analysis of the PSG.

In order to establish an external benchmark to which the NightOwl and PSG analysis could be compared, the codified PSG data will be transferred to Younes Medical Technologies Ltd. (YMT), the corporation behind the Michele Sleep Scoring System (MSSS) developed by [name]. Malhotra et al. confirmed that the MSSS, complemented with manual editing, standardizes PSG scoring results within and across sleep centers. Using such external benchmark, the impact of inter-scorer variability of current and future reports on NightOwl's performance metrics is reduced.

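### Pearson correlation is the only analysis specified for sleep time, and the only continuous one for REI, so a systematic misreading by NightOwl would go unmeasured

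*Combined protocol and SAP*

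**What the plan says.** Scientific objectives sets the aim for the index: "we will compare the respiratory event index (REI), defined as the number of respiratory events per hour of sleep, derived by the NightOwl system". The comparator is the manually scored PSG AHI, which the plan treats as its reference standard. On sleep time the same section says: "We will also compare the total sleep time (TST) derived by both systems". Justification for involving humans puts the question as "whether the NightOwl achieves adequate performance in deriving the REI".

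The methods are in Study analysis, which opens with "Two main performance analyses will be performed" and lists two:

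- The first is "The evaluation of the Pearson correlation between the REI and TST estimate obtained from the NightOwl", set against the AHI and sleep time from PSG.
- The second is categorical: "The evaluation of the agreement between patient categorization (into sleep apnea severity categories"), with NightOwl compared with manual PSG scoring. No agreement statistic and no cut-offs are given.

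The same section plans an external rescoring of the PSG as a benchmark, with no statistic attached. Nowhere does the document specify a mean difference, limits of agreement, a regression slope and intercept, an intraclass or concordance coefficient, or an acceptance limit. TST therefore has Pearson correlation alone. REI has Pearson correlation plus category agreement.

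**The concern.** The objectives ask whether the device gives the same values as PSG. Pearson's r answers a different question: how closely the two sets of values follow a straight line, whatever its intercept and positive slope.

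The gap is widest for TST. Every sleep time could be read an hour too long and the planned analysis would still report a high correlation, with no specified figure giving the offset.

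TST is also the denominator of REI as the plan defines it, so a sleep-time error can carry into the index. How much depends on how events in wake misread as sleep are counted, which the document does not say.

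For REI, a proportional under-reading moves patients into lower severity categories. The category analysis can register that, but no analysis states how many events per hour the device is off.

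**Working it through.** **Inputs.** The document gives 100 subjects (Number of subjects) and one paired night each (Frequency and duration). It gives no SDs, error sizes, target correlation or margin, so there is no stated figure to reproduce. Every other input below is an assumption, used only to show size.

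**1. Invariance of r.** For any constant a and any b > 0, corr(X, a + bY) = corr(X, Y). This is algebra and needs no assumption.

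**2. TST.** Assume a true SD of 60 min and an independent device error SD of 30 min.

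- r = 60/√(60² + 30²) = 60/67.1 = 0.894, the same with a +60 min offset. For SDs of 60 to 90 and error SDs of 20 to 40, r lies between 0.83 and 0.98, unaffected by any constant offset.
- 95% CI half-width of the mean difference at n = 100: 1.984 × 30/√100 = 6.0 min.
- Limits of agreement: mean difference ± 1.96 × 30 = ± 59 min. CI half-width of each limit: 1.984 × 30 × √(1/100 + 1.96²/198) = 10.2 min.
- Power of a paired t test to detect a 10-min offset:

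| Error SD (min) | CI half-width, mean (min) | CI half-width, each limit (min) | Power, 10-min offset |
|---|---|---|---|
| 20 | 4.0 | 6.8 | 99.9% |
| 30 | 6.0 | 10.2 | 91% |
| 40 | 7.9 | 13.6 | 70% |

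**3. Carry-over from TST to REI.** With the event count unchanged, a 60-min over-read multiplies REI by TST/(TST + 60):

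- 240/300 = 0.80
- 360/420 = 0.86
- 480/540 = 0.89

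If events in the extra hour are counted at a fraction f of the true rate, the factor at 360 min is (360 + 60f)/420. That is 0.93 at f = 0.5 and 1.00 (no effect) at f = 1.

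**4. REI.** Simulation with AHI lognormal (median 15/h, log-SD 0.95, capped at 120), error SD of 1.5 + 0.2 × AHI, and cut-offs of 5, 15 and 30/h. The device reads 0.857 × AHI, with the error either (a) scaled along with the reading or (b) left fixed. The unchanged r in (a) holds by construction.

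| | Unbiased | 0.857, (a) | 0.857, (b) |
|---|---|---|---|
| Pearson r | 0.95 | 0.95 | 0.93 |
| Same category | 75% | 73% | 70% |
| Moved down / up | 14% / 11% | 22% / 5% | 23% / 6% |
| Sensitivity at 15/h | 90% | 82% | 81% |
| Mean difference (events/h) | 0 | -3.2 | -3.2 |
| 95% CI half-width, n = 100 | – | 1.4 | 1.6 |

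In trials of n = 100, a sign test on the direction of misclassification would reject in 90% (a) or 87% (b). The CI of the mean difference would exclude zero in 99.8% (a) or 98.8% (b).

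**The case against.** The strongest reply concerns REI. The category analysis is already planned, and if the full cross-table is reported, a 14% under-reading would usually show in the direction of misclassification (90% or 87% of trials). That stands: what REI mainly lacks is the size of the error. It depends on reporting, though. The plan names no category statistic, and overall percent agreement alone moves only from 75% to 73% or 70%.

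A second reply is that a single mean difference does not fully describe a proportional error. In the scenario above, -3.2/h averages over roughly -0.7/h at an AHI of 5 (0.143 × 5) and -8.6/h at an AHI of 60 (0.143 × 60). This is fair, and it argues for a ratio or a regression on level alongside the mean difference.

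Third, any TST error that reaches REI is already inside the REI-versus-AHI comparison, and the carry-over may be nil. That also stands, so the case rests mainly on TST itself.

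Fourth, the precision figures assume 100 usable pairs, while the risk section lets subjects detach an uncomfortable sensor. With 80 pairs the TST half-width would be 1.990 × 30/√80 = 6.7 min instead of 6.0, which changes little.

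Finally, calling these the main analyses leaves room for others, but none is specified. An agreement analysis chosen after the data are seen is weaker evidence than one fixed beforehand.

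**Conclusion.** The concern holds and should be fixed. Followed as written, the plan would leave a constant or proportional TST error with no measure, and would leave an REI error without a size in events per hour. The central point is exact and rests on no assumed input. The sizes (an r of 0.894 unmoved by a 60-min offset, and an REI bias of about -3.2/h with r at 0.93 to 0.95) depend on the assumed distributions, error models and cut-offs. Nothing in the document suggests that NightOwl actually misreads by these amounts. The data themselves remain sound; only the analysis specification falls short.

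**What to change.** In Study analysis, make the main continuous analysis, for REI against AHI and for TST against TST, the mean paired difference and 95% limits of agreement, each with a 95% confidence interval. Use a log or ratio scale, or regression-based limits, where the spread grows with the level, and write down the rule for choosing beforehand. For REI, also report the ratio or the slope of the difference on level, so that constant and proportional error can be told apart. Keep Pearson's r as a descriptive figure. Limits of agreement will not by themselves settle whether performance is adequate, because the plan states no acceptance limit.

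The cost is one or two sentences and a few lines of code on paired data already being collected, with no extra subjects or procedures. The drawbacks are slightly more analysis and figures that may look less favourable than r alone.

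### Pearson correlation is the only continuous comparison of REI with AHI and of TST with TST; its size depends on case mix, and it does not give the error in events per hour

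*Combined protocol and SAP*

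**What the plan says.** The Study analysis section of the combined protocol and SAP opens with "Two main performance analyses will be performed" and lists two.

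- The first is "The evaluation of the Pearson correlation between the REI and TST estimate obtained from the NightOwl" with the AHI and TST from the PSG. The text gives no scale or transformation, severity strata, bias, limits of agreement, confidence interval or acceptance value.
- The second is "The evaluation of the agreement between patient categorization (into sleep apnea severity categories) obtained by the NightOwl" and by the manual PSG reading. It gives no cut-offs, agreement statistic or criterion.

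Three other places bear on the point. Scientific objectives says the study will "compare the respiratory event index (REI), defined as the number of respiratory events per hour of sleep", so the index is a rate in events per hour. Inclusion criteria admits "Subjects with an indication for an in-lab polysomnography", with no severity quota and no expected AHI distribution. Justification for involving humans gives the aim as finding out "whether the NightOwl achieves adequate performance in deriving the REI". The planned number of subjects is 100, without a supporting calculation.

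**The concern.** The stated aim is a question of accuracy: how far the device reading lies from the PSG reading. Pearson r answers a different question, namely how closely the points follow some straight line relative to the spread of the sample. Two consequences matter here.

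- The same device with the same error gives a different r in a clinic with a different severity mix. Since the protocol does not control or predict that mix, the value of r cannot be read as a property of the device.
- A high overall r can coexist with poor accuracy among patients with lower AHI, because the contrast between low and high AHI can carry the correlation.

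At stake is whether the main continuous result can support a statement that the device derives the REI adequately. TST has the same weakness, and no second analysis covers it.

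**Working it through.** **Inputs from the documents.** N = 100; Pearson correlation; index in events per hour; enrolment of anyone referred for PSG. There is no planned value of r and no calculation behind N, so the plan has no figure to reproduce.

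**Assumptions, not in the documents.** Device error SD 8 events/h for REI and 40 min for TST; AHI lognormal with median/log-SD of 10/1.0, 15/0.8, 15/1.0, 15/1.2 or 20/1.0, capped at 120; category cut-offs 5, 15 and 30.

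**Step 1: dependence on case mix.** If REI = AHI + error, with error independent of AHI, then r = s / √(s² + e²), where s is the SD of AHI and e the SD of the error. With e = 8:

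| SD of AHI | Calculation | r |
|---|---|---|
| 5 | 5/√(25 + 64) | 0.53 |
| 8 | 8/√(64 + 64) | 0.71 |
| 15 | 15/√(225 + 64) | 0.88 |
| 25 | 25/√(625 + 64) | 0.95 |

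The device is identical in every row. For TST with e = 40 min, a PSG TST SD of 60 min gives 60/√(3600 + 1600) = 0.83, and an SD of 110 min gives 110/√(12100 + 1600) = 0.94.

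**Step 2: the same error within severity ranges.** In simulated studies of 100 subjects (2,000 replicates, median 15, log-SD 1.0, error SD 8, REI floored at zero), r averages 0.95 overall, 0.69 below AHI 30 and about 0.42 below AHI 15.

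**Step 3: a high r with no information at lower AHI.** Take a device that is exact at AHI 30 and above, with its readings randomly permuted among patients below 30. This is a deliberate extreme. Mean r over the same number of replicates:

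| Median / log-SD | Share of patients below 30 | r |
|---|---|---|
| 10 / 1.0 | 86% | 0.85 |
| 15 / 0.8 | 81% | 0.86 |
| 15 / 1.0 | 76% | 0.92 |
| 15 / 1.2 | 72% | 0.95 |
| 20 / 1.0 | 66% | 0.95 |

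**Step 4: why the limits should depend on AHI level.** If the error SD were 2 + 0.2 × AHI (assumed), then at median 15 and log-SD 1.0 the pooled 95% limits would be about ±16 events/h. The actual limits would be about ±7 below AHI 15 and about ±28 at 30 or above. One pooled pair of limits would then be too wide for mild patients and too narrow for severe ones.

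**Step 5: precision of the replacement.** The relative 95% precision of an SD is about 1.96/√(2(n − 1)). For n = 100 this is 1.96/√198 = 14%; for n = 30 it is 1.96/√58 = 26%. A pooled limit from 100 subjects has a 95% margin of 1.96 × √(1/100 + 1.96²/198) = 0.34 SD, or about ±2.7 events/h if the SD is 8.

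**The case against.** The strongest reply is that r does not stand alone. The second main analysis compares severity categories, so a reader who infers that the plan ignores accuracy at category boundaries goes too far. That analysis could expose the device in Step 3. At median 15, log-SD 1.0 and the assumed cut-offs, linear-weighted kappa is 0.49 for the permuted device against 0.64 for the device with error SD 8, and 9% against 2% of patients are misplaced by two or more categories. Exact agreement separates them less well: 54% against 61%, with a standard error near 5 points for each. The plan does not say which statistic it will use. This reply stands in part. It softens the criticism, but category agreement does not give the size of the error in events per hour and does not address TST.

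It is also fair to say that analysis on the raw scale and over all subjects together is inferred from silence. It is the natural reading, and nothing in the documents contradicts it.

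Two stronger readings are tempting and are not supported.

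- A reader might infer that a few very severe patients decide the result. That depends on an AHI distribution and error structure the documents do not give. Removing the five highest AHIs lowered r by between 0.01 and 0.14 across the settings tried. Under the growing-error model of Step 4, removing the top 10% moved r only from 0.95 to about 0.91. Recomputing r without the top values is also a weak diagnostic: it still gave the permuted device anything from about 0.26 to 0.84.
- A reader might infer that r would fail to carry over to home-test patients. Scientific objectives cites home testing as background and places this study in a sleep laboratory. The plan claims no such transfer and gives no severity range for home-test patients.

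The external re-scoring of the PSG addresses scorer variability, not this point.

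**Conclusion.** The point holds as a cheap improvement to the analysis text. Pearson r is the only continuous comparison for both REI/AHI and TST, and it does not by itself answer the stated question of adequacy. The case-mix effect follows from algebra, given error independent of AHI: with an assumed error SD of 8 events/h, r runs from 0.53 to 0.95 as the AHI SD goes from 5 to 25. The finding that r of about 0.85 to 0.95 is compatible with no information below AHI 30 rests on the assumed lognormal distributions and on a constructed extreme. It shows what r permits, not what this device does. Whether the error grows with AHI is unknown, which is a reason to let the analysis estimate it.

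**What to change.** In Study analysis:

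1. Keep Pearson r for REI/AHI and for TST as descriptive, with the SD of PSG AHI and of PSG TST printed beside it.
2. Make the main continuous REI/AHI analysis the paired difference, REI minus AHI. Report bias and 95% limits of agreement, with confidence intervals, as a function of AHI level, either by letting the SD of the difference vary with the mean of the two readings or by analysing log(x + 1).
3. Report these at the severity cut-offs. The documents define none, so the sponsor must name them in advance; the category analysis needs them anyway.
4. Report bias and limits of agreement for TST minus TST, with confidence intervals.

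The cost is wording only: no new subjects, data or procedures. The downside is precision. If about 30 subjects inform a given AHI region (an illustrative number), the SD there is known to about ±26%, against ±14% when all 100 are pooled. The headline result may also look less favourable than a single correlation.
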